6.1.1.2.1 DLT Definition

A DLT is defined as any adverse event meeting the criteria listed below occurring during the first treatment cycle of AMG 510 (day 1 through day 21) where relationship to AMG 510 cannot be ruled out.

The grading of adverse events will be based on the guidelines provided in the CTCAE version 5.0. A DLT is defined as any of the following events during the first treatment cycle and attributable to AMG 510:

- Hematological toxicity
 - Febrile neutropenia
 - Neutropenic infection
 - Grade 4 neutropenia
 - Grade ≥ 3 thrombocytopenia for > 7 days
 - Grade 3 thrombocytopenia with grade ≥ 2 bleeding
 - Grade 4 thrombocytopenia
 - Grade 4 anemia
- Non-hematological toxicity
 - Grade ≥ 4 vomiting or diarrhea
 - Grade 3 diarrhea or grade 3 vomiting lasting more than 3 days despite optimal medical support
 - Grade ≥ 3 nausea for 3 days or more despite optimal medical support
 - Any other grade ≥ 3 adverse event

DLT-evaluable is defined as completion of 80% of AMG 510 doses within the first treatment cycle (ie, 21 days). A subject who experience a DLT within the first cycle is DLT evaluable regardless of number of doses taken. If a subject is withdrawn from study for any reason other than a DLT prior to completion of the 21-day safety

observation period, a replacement subject will be assigned the same dose as the replaced subject.

6.1.1.3 Dosage Adjustments, Delays, Rules for Withholding or Restarting, Permanent Discontinuation

Subjects experiencing any treatment-related toxicity meeting the DLT definition will not receive additional AMG 510 treatment and will be followed until resolution of the event or toxicity. Subjects will be withdrawn from AMG 510 treatment and will be treated as deemed appropriate by the investigator or treating physician. In subjects with a favorable response to treatment, an option to continue at the same dose level or 1 dose level below that which the toxicity occurred can be considered. If deemed appropriate by the investigator in conjunction with the sponsor, AMG 510 treatment can resume once any non-hematological toxicity returns to the subject's baseline value or grade ≤ 1 and subject meets the following hematological requirements: ANC $\geq 1.0 \times 10^9/L$, platelet count $\geq 75 \times 10^9/L$ and hemoglobin ≥ 9 g/dL. Subjects must not have received a platelet transfusion for at least 7 days prior to assessing if re-exposure to AMG 510 can occur.

If a subject is noted to have \geq grade 3 thrombocytopenia, grade 4 neutropenia, grade 4 anemia, grade 4 leukocytosis, or \geq grade 3 non-hematological toxicity attributable to AMG 510 at any point during study treatment, AMG 510 administration will be stopped immediately. A repeat blood collection for hematology is to be performed within 3 days. AMG 510 treatment can resume once subjects meet the following hematological requirements: ANC $\geq 1.0 \times 10^9/L$, platelet count $\geq 75 \times 10^9/L$ and hemoglobin ≥ 9 g/dL, leukocytosis $<$ grade 3 and the non-hematological toxicity returns to the subject's baseline value or grade ≤ 1 . Subjects requiring more than 2 weeks to recover from grade ≥ 3 toxicities will be **permanently discontinued** from the study **treatment**.

[REDACTED]

Approved

[REDACTED]

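### Protocol 6.1.1.3: outside the phase 1 DLT rule, AMG 510 can be restarted on a recently transfused platelet count, because the 7-day transfusion-free condition stands only in the DLT paragraph

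*Supplement*

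**What the plan says.** All references are to the current protocol (Amendment 3) unless stated.

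**First paragraph of 6.1.1.3 (DLTs).** The default is withdrawal: "Subjects experiencing any treatment-related toxicity meeting the DLT definition will not receive additional AMG 510 treatment". Continuing at the same dose level or one level lower is an option for subjects who are responding. Restart is a joint decision: "If deemed appropriate by the investigator in conjunction with the sponsor, AMG 510 treatment can resume once any non-hematological toxicity returns" to baseline or grade 1 and the ANC, platelet and hemoglobin thresholds are met. It adds: "Subjects must not have received a platelet transfusion for at least 7 days prior to assessing if re-exposure" can be considered.

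**Second paragraph of 6.1.1.3 (listed severe events).** The triggers are attributable thrombocytopenia of grade 3 or worse; neutropenia, anemia or leukocytosis of grade 4; and non-hematological toxicity of grade 3 or worse. When one occurs "at any point during study treatment, AMG 510 administration will be stopped immediately". Then: "A repeat blood collection for hematology is to be performed within 3 days", and "AMG 510 treatment can resume once subjects meet the following hematological requirements", with the same ANC, platelet and hemoglobin thresholds as in the first paragraph, plus leukocytosis below grade 3 and non-hematological recovery. Permanent discontinuation follows if a grade 3 or worse toxicity takes more than 2 weeks to recover.

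**DLT definition (6.1.1.2.1).** "A DLT is defined as any of the following events during the first treatment cycle and attributable to AMG 510", followed by 7 hematological and 4 non-hematological criteria. One is "Grade ≥ 3 thrombocytopenia for > 7 days"; others are grade 3 thrombocytopenia accompanied by bleeding of grade 2 or worse, and grade 4 thrombocytopenia. The parent section, 6.1.1.2, is headed as applying to phase 1 only, and section 10.1.2.1 ties the DLT analysis to phase 1. The heading of 6.1.1.3 carries no phase limit.

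**The concern.** A platelet count taken soon after a transfusion shows what was transfused, not whether the marrow has recovered. The sponsor guards against this for DLTs by requiring 7 transfusion-free days. The second paragraph deals with the same toxicity at the same platelet threshold but has no such guard, and no reason is given for the difference. A site that follows it to the letter may re-expose a subject whose thrombocytopenia has not resolved.

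There is also a smaller drafting gap. The second paragraph applies throughout treatment, cycle 1 included, and does not exclude DLTs. Many DLTs therefore fall under both paragraphs: one withdraws the subject unless investigator and sponsor agree otherwise, and the other allows resumption on recovery without naming the sponsor. No visible sentence says which prevails.

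**Working it through.** No sample size, power or error rate is involved. The check sets the two paragraphs side by side and counts the overlap.

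**1. Restart conditions**

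| Condition | DLT paragraph | Second paragraph |
|---|---|---|
| Default | Withdrawn from AMG 510 | Stopped; may resume on recovery |
| Investigator with sponsor | Required | Not named |
| ANC at least 1.0, platelets at least 75 (x 10^9/L), hemoglobin at least 9 g/dL | Yes | Yes |
| Non-hematological recovery to baseline or grade 1 | Yes | Yes |
| 7 days free of platelet transfusion | Yes | **Absent** |
| Repeat hematology within 3 days | Not named | Yes |
| Leukocytosis below grade 3 | Not named | Yes |

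**2. Thrombocytopenia governed by the second paragraph alone.** Its trigger is any attributable grade 3 or worse event. Taking out the three thrombocytopenia DLT criteria leaves:
- any event after day 21;
- in cycle 1, grade 3 lasting 7 days or less without bleeding of grade 2 or worse;
- all events in phase 2, on the natural reading that the DLT definition is confined to phase 1.

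**3. Timing.** Assume that the transfusion is given on the day of the event and that restart rests on the repeat count, due by day 3. The DLT paragraph would not let re-exposure be assessed before day 7. The difference is 7 - 3 = 4 days, so restart can come at least 4 days sooner under the second paragraph.

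**4. Overlap of the triggers.** Criteria listed: 7 + 4 = 11. Febrile neutropenia and neutropenic infection do not meet the second paragraph's trigger unless a listed grade is also present. The other criteria always do: grade 4 neutropenia, the three thrombocytopenia entries, grade 4 anemia and the four non-hematological entries, 1 + 3 + 1 + 4 = 9. So 9 of 11 criteria meet both triggers. This counts list entries; the documents give no frequencies for the criteria.

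**5. Could a ranking sentence be hidden?** Redacted text follows the second paragraph, so this cannot be fully excluded. It is unlikely. The table of contents shows a separate redacted entry between 6.1.1.3 and 6.2, and the unredacted 6.1.1.3 of Amendment 1 has the same two paragraphs with no ranking sentence.

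**6. Expected frequency.** Section 2.5 names renal toxicity, anemia, leukocytosis and splenomegaly as key safety information, not thrombocytopenia. Section 2.6.2.1 reports no DLT in 22 treated subjects at 180 to 720 mg and no significant hematology trend. If all 22 were DLT-evaluable, the exact two-sided 95% upper limit for the DLT rate is 1 - 0.025^(1/22) = 0.154, or 15.4%. That limit is for any DLT, not for thrombocytopenia, and there were no data yet at 960 mg.

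**The case against.** The strongest reply concerns the two defaults. The DLT paragraph is mandatory and the second is only permissive. Permission to resume does not cancel an instruction to withdraw, so a site that follows the DLT paragraph breaches nothing in the other. The common thresholds are identical. A phase 1 DLT also does not stay local: it moves later cohort dosing to the Bayesian model (3.1.1.1.1), and it is reviewed by the medical monitor, the safety officer and the investigators (6.1.1.2 and 10.4.1.1). This stands. A reader might infer that the paragraphs contradict each other, so that some sites would restart DLT subjects without the sponsor's knowledge. The documents do not support that; they show an unstated priority whose better reading is clear.

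The second reply is that harm needs several things at once: attributable grade 3 or worse thrombocytopenia, a recent platelet transfusion, and a discretionary restart on the transfused count. The toxicology summary (2.3.3) lists no platelet effect and reports no overt bone marrow toxicity. This also stands, and it sets the severity. It does not supply the missing condition. The protocol gives no reason why a safeguard thought necessary for DLTs should lapse for the same toxicity after day 21 or in phase 2.

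**Conclusion.** The omission is real, and it does not depend on how the priority question is settled: outside the phase 1 DLT rule, the text permits re-exposure on a recently transfused count of at least 75 x 10^9/L. The priority gap, touching 9 of 11 DLT criteria, is secondary. Overall the point is minor.

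It would be tempting to size it by the share of treatment time outside the 21-day window, or by the approximately 200 planned phase 2 subjects. Those figures describe where the rule applies, not how many subjects would be affected; that number cannot be derived from the documents. Nor does the point reach the main results. A subject with a DLT is evaluable whatever number of doses was taken (6.1.1.2.1), so MTD estimation is untouched, and no effect on ORR is shown.

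The conclusion assumes that the DLT definition is confined to phase 1, as its placement indicates, and that the redacted text holds no relevant rule. The 4-day figure further assumes a transfusion on the day of the event and a restart based on the repeat count.

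**What to change.** In 6.1.1.3:
1. Add the 7-day platelet-transfusion-free condition to the second paragraph.
2. State that for phase 1 events meeting the DLT definition the first paragraph prevails, and that the second governs its other listed events, including in phase 2. Wording it as governing every other event would be wrong, since it covers only a listed set.
3. State whether the transfusion-free wait counts toward the 2-week recovery limit. That limit is already worded generally and need not be repeated, but the two can collide: a subject transfused on day 8 after onset cannot be assessed before day 8 + 7 = 15, past the 14-day limit. Saying that the wait alone does not count is the simpler choice.

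The cost is a few sentences and a note to sites, with no added subjects or procedures. A few restarts would be delayed by up to 7 days. If the 2-week limit is kept strict, an occasional late-transfused subject would be discontinued.

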6.3 Hepatotoxicity Stopping and Rechallenge Rules (for Phase 1 and Phase 2)

Refer to [Appendix F](#) for details regarding drug-induced liver injury guidelines, as specified in the Guidance for Industry Drug-Induced Liver Injury: Premarketing Clinical Evaluation, July 2009.

6.4 Prior Therapies

Prior anticancer therapies must date back to the original diagnosis and will be collected through enrollment on the appropriate eCRF. For prior anticancer therapies collect line of therapy, regimen/agent, type of therapy, setting, start date, stop date, reason for stopping therapy, dose, unit, route, frequency, best response, date of best response, and date of progression documented. For prior radiotherapy for current malignancy, collect body site, sub site, setting, type, start date, stop date, total dose, unit, best response, was chemotherapy part of concurrent therapy, did documented progression occur in this area, date progression documented. For prior surgeries for current malignancies collect date of surgery, surgery, reason for surgery, body site, subsite, intent of surgery, residual disease.

All other prior therapies that were being taken 28 days before enrollment through enrollment should be collected on each subject's eCRF(s). Collect therapy name, indication, dose, unit, frequency, route, start date and stop date.

6.5 Concomitant Therapy (for Phase 1 and Phase 2)

Throughout the study, Investigators may prescribe any concomitant medications or treatments deemed necessary to provide adequate supportive care except for those listed in [Section 6.5](#).

Approved

Concomitant use of MATE1 substrates with AMG 510 may result in increase in systemic concentrations of a MATE1 substrate as AMG 510 has a potential to inhibit MATE1. Gastric acid controllers may reduce the exposure to AMG 510. Consider the risks and benefits of concomitant use. Monitor subjects receiving a MATE1 substrate or gastric acid controller with AMG 510.

In the phase 1 part of the study, Amgen will review all concomitant medications with the investigators prior to dosing with AMG 510 to ensure patient safety.

Concomitant therapies are to be collected from enrollment through the end of safety follow-up period.

For concomitant therapies, collect therapy name, indication, dose, unit, frequency, route, start date and stop date.

6.6 Product Complaints (for Phase 1 and Phase 2)

A product complaint is any written, electronic or oral communication that alleges deficiencies related to the identity, quality, durability, reliability, safety, effectiveness, or performance of a drug(s) or device(s) after it is released for distribution to market or clinic by either Amgen or by distributors and partners for whom Amgen manufactures the material.

This includes any drug(s), device(s), or combination product(s) provisioned and/or repackaged /modified by Amgen. Drug(s) or device(s) includes investigational product.

Any product complaint(s) associated with an investigational product(s) or non-investigational product(s) or device(s) supplied by Amgen are to be reported according to the instructions provided in the IPIM.

6.7 Excluded Treatments, Medical Device Use, and/or Procedures During Study Period (for Phase 1 and Phase 2)

The following medications and supplements to be avoided for 14 days prior to enrollment and during the study period unless reviewed and approved by the principal investigator and the Amgen medical monitor:

- Known strong inhibitors of cytochrome P450 (CYP) 3A4 or P-gp including herbal supplements such as Goldenseal and grapefruit juice or other grapefruit containing products
- Known strong inducers of cytochrome P450 (CYP) 3A4 including herbal supplements, such as St. John's wort
- Known cytochrome P450 (CYP) 3A4 and MATE1 sensitive substrates with a narrow therapeutic window

If a subject needs palliative radiotherapy for pain control during the course of the study, all study drugs should be discontinued, and the investigator or designee should notify the sponsor as soon as possible. A subject may be allowed to resume study drug after discussion between the Amgen medical monitor and the investigator to determine the appropriateness of treatment resumption.

Subjects must not schedule any major elective surgeries during the treatment period, and for at least 28 days after the last administration of AMG 510. Minor elective surgery may be allowed after discussion with the Amgen medical monitor. If a subject undergoes any unexpected surgery during the course of the study, all study drugs must be discontinued, and the investigator or designee should notify the sponsor as soon as possible. A subject may be allowed to resume AMG 510 [REDACTED] [REDACTED] only if both the investigator and Amgen medical monitor agree to restart study therapy.

7. STUDY PROCEDURES

7.1 Schedule of Assessments

Approved

Table 2. Schedule of Assessment: Phase 1 Part 1 Dose Exploration and Part 2 Dose Expansion

	Screen ^a	Treatment																		EOT ^b	SFU	LTFU									
Cycle		1												2				3,5	4,6	QC	Q2C										
Day	-28 to 1	1				2	8				9	15	1		8	1	1	1	1												
Hours (relative to dosing)		pre	0	0.25	0.5	1	2	4	6	pre	0	pre	0	0.25	0.5	1	2	4	6	pre	0	pre	0	pre	0	0.25	0.5	1			
GENERAL & SAFETY																															
Informed consent	X																														
Eligibility criteria	X																														
Demographics	X																														
Medical history & height	X																														
Smoking status	X																														
Physical exam & weight	X	X									X												X	X							
ECOG	X	X																					X								
Vital signs	X	X	X	X	X	X	X	X	X	X	X	X	X	X	X	X	X	X	X	X	X	X	X	X	X	X	X	X	X	X	X
ECG ^c	X	X	X	X	X	X	X	X	X	X	X	X	X	X	X	X	X	X	X	X	X	X	X	X	X	X	X	X	X	X	X
Prior therapies	X																														
Anticancer therapy																															
Con medications		X	←=====→																												
Adverse events			←=====→																												
Serious adverse			←=====→																												

Approved

Footnotes defined on last page of the table

Table 2. Schedule of Assessment: Phase 1 Part 1 Dose Exploration and Part 2 Dose Expansion

	Screen ^a	Treatment																EOT ^b	SFU	LTFU																
Cycle		1								2								3,5,6	QC	Q2C																
Day	-28 to 1	1				2	8				9	15	1				8	1	1	1	1															
Hours (relative to dosing)		pre	0	0.25	0.5	1	2	4	6	pre	0	pre	0	0.25	0.5	1	2	4	6	pre	0	pre	0	pre	0	0.25	0.5	1								
PK ASSESSMENTS																																				
AMG 510 PK ^l		X	X	X	X	X	X	X	X	X	X		X	X	X	X	X	X	X			X		X	X	X		X								
BIOMARKER SAMPLES																																				
Tumor markers at site ^m		(X)																																		
Cell pellet from plasma ⁿ		X																																		
Plasma ctDNA ^o		X								X										X						X	X	X			X					
Serum		X								X										X						X	X	X			X					
PB Paxgene RNA		X								X										X						X	X	X			X					
Stool sample ^p		X																														X				
BIOMARKER DEVELOPMENT																																				
Tumor biopsy (optional, as applicable) or archived tumor tissue (FFPE) for solid tumors		X ^q																																(X) ^r		

Approved

Footnotes defined on next page

BID = twice daily; CNS = central nervous system; **Con = concomitant**; CT = computed tomography; cfDNA = cell-free DNA; ECG = electrocardiogram; ECOG = Eastern Cooperative Oncology Group; EOT = end of treatment; FFPE = formalin-fixed paraffin-embedded; HbA1c = hemoglobin A1c; LTFU = long-term follow-up; MRI = magnetic resonance imaging; NSCLC = non-small cell lung carcinoma; PD-L1 = programmed cell death-1; PET = positron emission tomography; **PB = peripheral blood**; PK = pharmacokinetic(s); QC = every cycle from cycle 7 and beyond (cycles 7, 8, 9, etc), Q2C = every other cycle from cycle 7 and beyond (cycles 7, 9, 11 etc); **Screen = screening**; SFU = safety follow-up.

(X) = Parentheses indicate that the particular test is situational at that time point, as specified in the respective notes.

^a **KRAS p.G12C testing** results must be available prior to starting all other screening procedures; PD-L1 testing in NSCLC for **Part 1c and 2c**.

^b **For subjects who discontinue investigational product, the EOT visit should occur as soon as possible (within 14 days) after the last dose of investigational product.**

^c **Three** triplicate ECGs must be performed at screening. **For all other visits, one triplicate ECG must be performed.** Each tracing must be at least 30 seconds apart.

^d Assessments to be performed on day 1 of each cycle. Laboratory assessments may be performed within 24 hours before day 1 of each cycle. A window of ± 1 day is allowable for cycle 1 and cycle 2. A window of ± 2 days is allowable after cycle 2. Electrocardiograms, biomarker blood draws, safety labs, vital signs (including pulse oximetry): ± 5 -minute window (for time points of 0.25 hr and 0.5 hr postdose), ± 15 -minute window (all other time points).

^e Microscopic exam required to be performed with each time point collected.

^f **For women of childbearing potential only (defined in Criterion 215 in Section 4.2).**

^g AMG 510 will be administered daily on a repeated basis with no planned off treatment days. AMG 510 must be administered in the fasted state (no food or liquids, except water, 2 hours before to 1 hour after dosing).

ⁱ Radiological imaging and tumor assessments are required at screening and every 6 ± 1 weeks. After **four** 6-week response assessments, radiological imaging and tumor assessments will be performed every 12 ± 1 weeks. Imaging and tumor assessments will continue until disease progression, start of new anticancer treatment, death, withdrawal of consent, or until end of study. MRI/CT scans can be obtained earlier if clinical deterioration necessitates an earlier scan at the discretion of the managing physician. End of treatment CT/MRI should be performed only for subjects that discontinue treatment for a reason other than disease progression per **RECIST 1.1** criteria. Every assessment must include the chest, abdomen, pelvis, and all other known sites of disease. Tumor burden assessments will be performed based on **RECIST 1.1** guidelines ([Appendix D](#)). Radiographic response (CR and PR) requires confirmation by a repeat consecutive assessment 4 weeks after the first detection of response.

^j **For subjects who discontinued study treatment without confirmed disease progression or start of subsequent anticancer treatment, tumor assessments will continue during LTFU every 12 weeks (± 2 weeks) for up to 3 years after last subject enrolled or until confirmed disease progression, start of subsequent anticancer treatment, death, withdrawal of consent, loss to follow-up, or end of study.**

^k All subjects with history of brain metastases must have MRI of the brain performed within 28 days prior to enrollment. Only if MRI is contraindicated, then CT with contrast is acceptable. Subsequently, MRI brain scans can be performed at any time if clinically indicated or per standard of care. Any additional imaging used to evaluate or determine response (eg, PET, CT/PET, bone scan, etc) should be sent along with the required imaging to the central imaging vendor promptly upon completion.

^l Pharmacokinetic blood samples should be collected at the exact nominal time point as noted above (see hour postdose column). If unable to collect a blood sample at the specified nominal time point, collect it as close as possible to the nominal time point and record the actual collection time. Pharmacokinetic samples not collected at exact nominal time point will not be considered protocol deviations. Pharmacokinetic samples collected in cycle 3 and beyond should be performed prior to AMG 510 dosing.

^m Tumor markers will be performed as per standard of care and reported on the applicable eCRF.

ⁿ **Cell pellet will be used for pharmacogenetics analysis in subjects who consent.**

^o Plasma cfDNA is to be collected as indicated in the Schedule of Assessments, and at response.

^p **Stool samples collected predose (-3 days) and at EOT (± 3 days).**

Approved

^q Subjects should provide archived FFPE samples (collected within 5 years) or undergo tumor biopsy for exploratory analysis and which may include *KRAS p.G12C* mutation testing if local results are not available. PD-L1 testing will also be performed prior to enrollment for parts 1c and 2c.
^r After enrollment, optional tumor biopsy will be performed for subjects who consent to this assessment. It will be performed, if feasible, on cycle 1 day 8 at least 4 hours (± 2 hours) after dosing, at response, and at the EOT.

Table 3. Schedule of Assessment: Phase 1 Part 1a or Part 2a Food Effect Assessment Only

	Treatment																	
Cycle	2 or later																	
Day	1								2								3	
Hours (relative to dosing) ^a	pre	0	0.25	0.5	1	2	4	6	pre	0	0.25	0.5	1	2	4	6	pre	0
DOSING																		
AMG 510 ^b		X								X								X
PK ASSESSMENT																		
AMG 510 PK ^c	X		X	X	X	X	X	X	X		X	X	X	X	X	X	X	X
RENAL EXCRETION ASSESSMENT																		
Urine	X (0 to 6 hours)								X									

PK = pharmacokinetic(s).

^a Refer to Table 2 for assessments other than for dosing and PK and renal assessments on days 1 to 3.

^b Subjects will be administered AMG 510 on day 1 in the fasted state (no food 10 hours before dosing and 3 hours after dosing) and on day 2 in the fed state (dosing with a high fat meal). On day 3, AMG 510 can be administered with or without food per subject discretion.

^c Pharmacokinetic blood samples should be collected at the exact nominal time point as noted above (see hour postdose column). If unable to collect a blood sample at the specified nominal time point, collect it as close as possible to the nominal time point and record the actual collection time. Pharmacokinetic samples not collected at exact nominal time point will not be considered protocol deviations.

Approved

Table 4. Pharmacokinetic Schedule of Assessment: Phase 1 Part 1b Dose Exploration (BID dosing only)

	Screening	Treatment																								EOT					
		1												2		3,5 ^a		Q2C													
Day	-28 to 1	1				2	8								9	1		1	1												
Hours (relative to dosing) ^a		pre	0	0.25	0.5	1	2	4	6	12	pre	0	pre	0	0.25	0.5	1	2	4	6	12	pre	0	pre	0	0.25	0.5	1			
DOSING																															
AMG 510 ^b			X							X		X	X								X		X	X				X	X		
PK ASSESSMENTS																															
AMG 510 PK ^c		X		X	X	X	X	X	X	X	X		X		X	X	X	X	X	X	X	X		X		X	X	X	X	X	

BID = twice daily; EOT = end of therapy; PK = pharmacokinetic(s); Q2C = every other cycle from cycle 7 and beyond (cycles 7, 9, 11 etc).

^a Refer to Table 2 for assessments other than for PK.

^b AMG 510 will be administered **twice**-daily on a repeated basis with no planned off treatment days. AMG 510 must be administered in the fasted state (no food or liquids, except water, 2 hours before to 1 hour after dosing). On PK days (eg, cycle 1 day 1, cycle 1 day 8, and cycle 2 day 1), subjects should eat a standard meal at least 2 hours before dosing. [REDACTED]

^c Pharmacokinetic blood samples should be collected at the exact nominal time point as noted above (see hour postdose column). If unable to collect a blood sample at the specified nominal time point, collect it as close as possible to the nominal time point and record the actual collection time. Pharmacokinetic samples not collected at exact nominal time point will not be considered protocol deviations. Pharmacokinetic samples collected in cycle 3 and beyond should be performed prior to AMG 510 dosing.

Approved

Table 5. Schedule of Assessment: Phase 2 Study Visits Through Cycle 1 Treatment

	Screening ^a	Treatment																					
Cycle		1																					
Day	-28 to 1	1								2		8								9		15	
Hours (relative to dosing)		pre	0	0.25	0.5	1	2	4	6	pre	0	pre	0	0.25	0.5	1	2	4	6	pre	0	pre	0
GENERAL & SAFETY																							
Informed consent	X																						
Eligibility criteria	X																						
Demographics	X																						
Medical history & height	X																						
Smoking status	X																						
Physical exam & weight	X	X									X												X
ECOG	X	X																					
Vital signs	X	X								X	X												X
ECG (Group A) ^{b, c}	X	X		X	X	X	X	X	X	X		X		X	X	X	X	X	X	X		X	
ECG (Group B) ^{b, c}	X	X				X						X											
Prior therapies	X																						
Anticancer therapy																							
Con medications	X	X	←=====→																				
Adverse events		←=====→																					
Serious adverse events		←=====→																					
Patient diaries		←=====→																					

Approved

Footnotes defined on last page of [Table 6](#).

Table 5. Schedule of Assessment: Phase 2 Study Visits Through Cycle 1 Treatment

	Screening	Treatment																					
Cycle		1																					
Day	-28 to 1	1								2		8						9		15			
Hours (relative to dosing)		pre	0	0.25	0.5	1	2	4	6	pre	0	pre	0	0.25	0.5	1	2	4	6	pre	0	pre	0
Patient-reported Outcomes																							
EORTC QLQ C30		X																					
QLQ LC13		X																					
NSCLC SAQ		X																					
QLQ PAN26		X																					
PRO-CTCAE		X																					
EQ-5D-5L		X																					
GP5 FACT-G		X																					
Laboratory^d																							
Chemistry	X	X										X											X
HbA1c	X																						
Hematology	X	X										X											X
Coagulation	X	X										X											X
Urinalysis ^e	X	X										X											X
Serum pregnancy test ^f	X																						
Urine pregnancy test^f		X																					
HIV	X																						
Hepatitis serology	X																						

Approved

Footnotes defined on last page of [Table 6](#).

Table 5. Schedule of Assessment: Phase 2 Study Visits Through Cycle 1 Treatment

	Screening	Treatment																					
Cycle		1																					
Day	-28 to 1	1								2		8								9		15	
Hours (relative to dosing)		pre	0	0.25	0.5	1	2	4	6	pre	0	pre	0	0.25	0.5	1	2	4	6	pre	0	pre	0
DOSING																							
AMG 510 ⁹		←----->																					
IMAGING ASSESSMENTS																							
Radiological imaging, (CT/MRI) and tumor assessment ^h	X																						
MRI brain ⁱ	X																						
PK ASSESSMENTS																							
AMG 510 PK (Group A) ^j		X	X	X	X	X	X	X	X	X		X		X	X	X	X	X	X	X			
AMG 510 PK (Group B) ^j		X				X		X															
BIOMARKER SAMPLES																							
Tumor markers at site ^k		(X)																					
Plasma ctDNA ^l		X										X											
Cell pellet from plasma ^m		X																					

Approved

Footnotes defined on last page of [Table 6](#).

Table 5. Schedule of Assessment: Phase 2 Study Visits Through Cycle 1 Treatment

	Screening	Treatment																					
Cycle		1																					
Day	-28 to 1	1							2		8						9		15				
Hours (relative to dosing)		pre	0	0.25	0.5	1	2	4	6	pre	0	pre	0	0.25	0.5	1	2	4	6	pre	0	pre	0
BIOMARKER SAMPLES Cont.																							
Serum		X										X											
PB Paxgene RNA		X										X											
Stool sample ⁿ		X																					
BIOMARKER DEVELOPMENT																							
Tumor biopsy (optional, as applicable) or archived tumor tissue (FFPE) for solid tumors		X ^o																				X ^p	

Footnotes defined on last page of [Table 6](#).

Approved

Table 6. Schedule of Assessment: Phase 2 Study Visits Through Cycle 2 Treatment and LTFU

	Treatment											EOT	SFU	LTFU		
Cycle	2						8	3,5 ^a			4,6	QC	Q2C			
Day	1						8	1			1	1	1			
Hours (relative to dosing)	pre	0	0.25	0.5	1	4		pre	1	4						
GENERAL & SAFETY																
Physical exam & weight	X							X			X	X			X	
ECOG	X							X			X	X		X	X	
Vital signs	X															
ECG (Group A) ^{b, c}	X				X	X			X		X	X			X	
ECG (Group B) ^{b, c}															X	
Anticancer therapy															X	X
Concomitant medications	←-----→															
Adverse events	←-----→															
Serious adverse events	←-----→															
Patient diaries	←-----→															

Footnotes defined on last page of the table.

Approved

Table 6. Schedule of Assessment: Phase 2 Study Visits Through Cycle 2 Treatment and LTFU

	Treatment												EOT	SFU	LTFU	
Cycle	2						8	3,5			4,6	QC	Q2C			
Day	1						8	1			1	1	1			
Hours (relative to dosing)	pre	0	0.25	0.5	1	4		pre	1	4						
Patient-reported Outcomes																
EORTC QLQ C30	X							X			X		X	X	X	
QLQ LC13	X							X			X		X	X	X	
NSCLC SAQ	X							X			X		X	X	X	
QLQ PAN26	X							X			X		X	X	X	
PRO-CTCAE	X							X			X		X	X	X	
EQ-5D-5L	X							X			X		X	X	X	
GP5 of the FACT-G	X							X			X		X	X	X	
Laboratory^d																
Chemistry	X							X			X	X				
Hematology	X							X			X	X				
Coagulation	X							X			X	X				
Urinalysis ^e	X							X			X	X				
Serum pregnancy test ^f															X	
Urine pregnancy test^f	X							X			X	X				

Approved

Footnotes defined on last page of the table.

Table 6. Schedule of Assessment: Phase 2 Study Visits Through Cycle 2 Treatment and LTFU

	Treatment													EOT	SFU	LTFU
Cycle	2							3,5			4,6	QC	Q2C			
Day	1						8	1		1	1	1				
Hours (relative to dosing)	pre	0	0.25	0.5	1	4		pre	1	4						
DOSING																
AMG 510 ^g	←-----→															
IMAGING ASSESSMENTS																
Radiological imaging, (CT/MRI) and tumor assessment ^h								X						X	X	(X) ^a
MRI brain ⁱ																
PK ASSESSMENTS																
AMG 510 PK (Group A) ⁱ	X				X	X		X	X	X				X		
AMG 510 PK (Group B) ⁱ	X				X	X		X	X	X				X		
BIOMARKER SAMPLES																
Tumor markers at site ^k	(X)															
Plasma ctDNA ^l	X							X			X	X		X		
Cell pellet from plasma ^m																

Footnotes defined on last page of the table.

Approved

Table 6. Schedule of Assessment: Phase 2 Study Visits Through Cycle 2 Treatment and LTFU

	Treatment												EOT	SFU	LTFU
Cycle	2						3,5		4,6	QC	Q2C				
Day	1						1		1	1	1				
Hours (relative to dosing)	pre	0	0.25	0.5	1	4		pre	1	4					
BIOMARKER SAMPLES Cont.															
Serum	X							X			X	X		X	
PB Paxgene RNA	X							X			X	X		X	
Stool sample ⁿ														X	
BIOMARKER DEVELOPMENT															
Tumor biopsy (optional, as applicable)	(X) ^P												X ^P		

Footnotes defined on next page

Approved

CNS = central nervous system; CT = computed tomography; cfDNA = cell-free DNA; ECG = electrocardiogram; ECOG = Eastern Cooperative Oncology Group; EOT = end of treatment; FFPE = formalin-fixed paraffin-embedded; HbA1c = hemoglobin A1c; LTFU = long-term follow-up; MRI = magnetic resonance imaging; NSCLC = non-small cell lung carcinoma; PD-L1 = programmed cell death-1; PET = positron emission tomography; **PB = peripheral blood**; PK = pharmacokinetic; PRO-CTCAE = Patient-Reported Outcomes version of the Common Terminology Criteria for Adverse Events; QC = every cycle from cycle 7 and beyond (cycles 7, 8, 9, etc), Q2C = every other cycle from cycle 7 and beyond (cycles 7, 9, 11 etc); SFU = safety follow-up.

(X) = Parentheses indicate that the particular test is situational at that time point, as specified in the respective notes.

^a **KRAS p.G12C testing results must be available** prior to starting all other screening procedures

^b **Three triplicate ECGs must be performed at screening. For all other visits, one triplicate ECG must be performed. Each tracing must be at least 30 seconds apart.**

^c Intense ECG collection will be performed in up to approximately 30 subjects at time points described for Group A. Sparse ECG collection will be performed in the remaining subjects at time points described for Group B.

^d Assessments to be performed on day 1 of each cycle. Laboratory assessments may be performed within 24 hours before day 1 of each cycle. A window of ± 1 day is allowable for cycle 1 and cycle 2. A window of ± 2 days is allowable after cycle 2. Electrocardiograms, biomarker blood draws, safety labs, vital signs (including pulse oximetry): ± 5 minute window (for time points of 0.25 hour and 0.5 hour postdose), ± 15 -minute window (all other time points).

^e Microscopic exam required to be performed with each time point collected.

^f **For women of childbearing potential only (defined in Criterion 215 in Section 4.2).**

^g AMG 510 will be administered daily on a repeated basis with no planned off treatment days. AMG 510 must be administered in the fasted state (no food or liquids, except water, 2 hours before to 1 hour after dosing).

^h Radiological imaging and tumor assessments are required at screening and every 6 ± 1 weeks. After **four** 6-week response assessments, radiological imaging and tumor assessment frequency will be performed every 12 ± 1 weeks until disease progression, start of new anti-cancer treatment, death, or withdrawal of consent until end of study. MRI/CT scans can be obtained earlier if clinical deterioration necessitates an earlier scan at the discretion of the managing physician. End of treatment CT/MRI should be performed only for subjects that discontinue treatment for a reason other than disease progression per **RECIST 1.1** criteria. Every assessment must include the chest, abdomen, pelvis, and all other known sites of disease. Tumor burden assessments will be performed based on **RECIST 1.1** guidelines ([Appendix D](#)). Radiographic response (CR and PR) requires confirmation by a repeat consecutive assessment 4 weeks after the first detection of response.

ⁱ All subjects with history of brain metastasis must have MRI of the brain performed within 28 days prior to enrollment. Only if MRI is contraindicated, then CT with contrast is acceptable. Subsequently, MRI brain scans can be performed at any time if clinically indicated or per standard of care. Any additional imaging used to evaluate or determine response (eg, PET, CT/PET, bone scan, etc) should be sent along with the required imaging to the central imaging vendor promptly upon completion.

